One week after the injection, all patients received a prescribed exercise regimen to be performed in their own homes. The exercise routine encompassed self-stretching, joint mobility exercises, and strength-building activities. A designated physical therapist demonstrated the exercises to each patient individually, and an exercise booklet was provided to assist them.

Finally, the patients were advised to use paracetamol (500 mg) and/or naproxen (750 mg), if necessary. They were asked not to take analgesics at or 1 day before the follow-up points, as it could affect the clinical outcome measures.

Outcome Measures

All patients were evaluated for primary and secondary outcome measures before injection (baseline) and at 1, 4, and 12 weeks after injection by an investigator blinded to the injections. The primary outcome measure of the study was the Shoulder Pain and Disability Index (SPADI), while the secondary outcome measures were visual analog scale (VAS) scores, active range of motion of the shoulder (ROM), pressure pain thresholds (PPT), and treatment satisfaction. All adverse events that occurred during the procedure and at a follow-up visit were recorded.

Primary outcome measure: The Shoulder Pain and Disability Index is a shoulder-specific index consisting of 13 items that assess shoulder pain and disability on two different scales. Each item is scored between 0 and 10, and the resulting score is converted into a 100-point scale separately for pain, disability, and total score. Increased SPADI scores indicate an increase in patients' shoulder-related pain and disability. Patients with a reduction in the total SPADI score of 18 points or more from baseline to week 12 (the last follow-up) were considered treatment successes. (2). The SPADI has been shown to be valid and reliable in Turkish (3).

Secondary outcome measures: The VAS (0–10 range) was evaluated in each patient for night and activity. An additional VAS assessment was performed 1 h after the injection. Active

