shoulder ROM measurements of the patients were performed using a standard manual goniometer. Measurements were made in the supine position, and active forward flexion (FF), abduction (US), internal rotation (IR), and external rotation (ER) were measured. The IR and ER measurements were made with the shoulder abducted at 90°. The PPT measurements were obtained over the middle deltoid, upper trapezius, infraspinatus, and tibialis anterior muscles using a 1 cm diameter probe from an electronic digital display algometer (Commander Echo® Algometer, JTECH Medical, Midvale, UT, USA). Measurements were taken directly on the skin and vertically, and the patient was instructed to stop when the feeling of pressure first turned into a feeling of pain and discomfort. Three measurements were taken from each region, and the average of the last two measurements was recorded. The PPT values were expressed as kilograms per square centimeter (kg/cm²). A low PPT value represents a decrease in the pain threshold and, therefore, increased sensitivity. A 5-point Likert scale was used to evaluate the patients' overall satisfaction with the treatment (1= extremely dissatisfied, 2= dissatisfied, 3=neutral, 4= satisfied, and 5= extremely satisfied).

The patients' compliance with the exercise program was queried at the 4th and 12th weeks after the injection. The patients were asked to choose between "Never did," "I did it occasionally," and "I did it regularly." Finally, they were asked how much they used the paracetamol (500 mg) and naproxen (750 mg) that had been sent home with them after the injection at the 1st, 4th, and 12th weeks. The total amount of drug used was recorded.

Statistical Analyses

The sample size required for the research was calculated via a website (<http://statulator.com/SampleSize/ss2M.html>). In a previous study, the Minimal Clinically Important Difference (MCID) value for SPADI ranged from 8 to 13 points (2). We established our research hypothesis that the clinical results of SSNB at the level of the spinoglenoid notch would not be non-inferior to SSNB at the level of the suprascapular notch. Accordingly, when the non-inferiority margin is -9 and the standard deviation is 15.3; With 80% power and type 1 error 0.05, 36 patients in each group should be recruited. Assuming a 10% dropout rate, 40 patients were planned for each group.

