The collected data were statistically analyzed using IBM SPSS ver. 22.0 (IBM Corp., Armonk, NY, USA). All analyses were performed according to the "intention to treat" principle, and the missing data were completed using the single imputation method. The Shapiro-Wilk test, as well as histograms and QQ plots, were used to test whether the data were normally distributed. Analysis results were presented as mean \pm standard deviation for numerical data and as numbers and percentages for categorical data. For numerical data, the differences between groups were compared using the independent samples t-test or the Mann-Whitney U test. Categorical data were analyzed using chi-square tests or Fisher's exact test. In addition, the differences (Δ) between the baseline value of the outcome measures and the values at the follow-up time points were calculated and included in the intergroup comparison. The Friedmann test was used for intragroup comparisons of the changes in outcome measures from baseline to follow-up times. The post hoc Dunn-Bonferroni test was then used for

pairwise comparisons of follow-up times. A P value less than 0.05 was considered statistically significant.

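### If baseline is ranked with the follow-up visits, the within-arm Dunn-Bonferroni tests between follow-up visits are conservative; paired tests on the two visits would be a cheap improvement (minor)

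*Combined protocol and SAP*

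**What the plan says.** The Outcome Measures section sets the visits: "All patients were evaluated for primary and secondary outcome measures before injection (baseline) and at 1, 4, and 12 weeks after injection". VAS has one more reading: "An additional VAS assessment was performed 1 h after the injection".

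For change over time within an arm, the Statistical Analyses section states: "The Friedmann test was used for intragroup comparisons of the changes in outcome measures from baseline to follow-up times". It continues: "The post hoc Dunn-Bonferroni test was then used for" "pairwise comparisons of follow-up times. A P value less than 0.05 was considered statistically significant". The other tests named there (t-test, Mann-Whitney, chi-square, Fisher, and the comparison of differences from baseline) compare the two arms.

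The plan does not say whether baseline is itself one of the ranked visits, or whether the 1-hour VAS reading enters the ranking. It gives no correlation between visits and no expected fall after baseline.

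Two figures give a scale for SPADI change. The cited "Minimal Clinically Important Difference (MCID) value for SPADI ranged from 8 to 13 points", and the non-inferiority margin is 9 points.

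**The concern.** After a Friedman test, Dunn's procedure ranks all visits jointly within each patient and divides the difference in mean rank by a standard error fixed by the number of visits and patients. That standard error is correct when all visits have the same distribution. A comparison of week 4 with week 12 asks only whether those two visits differ.

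The two conditions part company when the injection works. Baseline then takes the worst rank in most patients, the follow-up visits share the remaining ranks, and their rank differences are compressed while the standard error stays the same. The answer for week 4 against week 12 then depends on how severe baseline was, which is irrelevant to that pair.

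A large response is not far-fetched here. Success is defined by "Patients with a reduction in the total SPADI score of 18 points or more from baseline to week 12", and 18 points exceeds the planning SD of 15.3. What is at stake is a real but modest return of symptoms between follow-up visits being reported as no significant change within an arm.

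**Working it through.** **Plan's own figure.** Sample size with margin 9, SD 15.3, 80% power and one-sided alpha 0.05: n = 2 × (1.645 + 0.842)² × 15.3² / 9² = 35.7, so 36 per group, and 36 / 0.9 = 40. Both stated numbers reproduce. Because the analysis is intention to treat with single imputation, 40 per arm is used below.

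**Standard error, with baseline ranked.**
- Visits k = 4, so 6 pairs. Adjusted level 0.05/6 = 0.0083, two-sided z = 2.638.
- Dunn standard error = √(k(k+1)/(6n)) = √(20/240) = 0.289. Mean-rank difference needed: 2.638 × 0.289 = 0.762.
- If baseline is the worst visit for every patient, only ranks 1–3 vary over follow-up. The null standard error for two follow-up visits is then √(12/240) = 0.224.
- Ratio: 0.289/0.224 = 1.29, so the standard error used is 29% too large. The effective cut-off is 2.638 × 1.29 = 3.41, a two-sided error of about 0.0007 instead of 0.0083.
- Let p be the share of patients worse at week 12 than at week 4, and likewise than at week 1, with weeks 1 and 4 alike. The expected mean-rank difference is 1.5 × (2p − 1). Setting this to 0.762 gives p = 0.75.

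This step needs no assumed data beyond baseline being the worst visit; 29% is the limiting case.

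**Power.** Simulation, n = 40 per arm, multivariate normal, SD 15.3 at each visit, equal correlation between visits. The visit means and the correlations are assumptions. Power for week 4 against week 12, both tests at 0.05/6, at correlations 0.3 / 0.5 / 0.7:

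| SPADI means (baseline, weeks 1, 4, 12) | Change | Dunn-Bonferroni | Paired signed-rank |
|---|---|---|---|
| 60, 34, 34, 43 | 9 | 35 / 49 / 75% | 63 / 80 / 97% |
| 70, 30, 30, 39 | 9 | 24 / 37 / 66% | 60 / 79 / 96% |
| 60, 35, 33, 41 | 8 | 25 / 35 / 60% | 47 / 65 / 90% |

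Repeat runs differ by a point or two, giving about 23–75% against about 47–97% overall. For a 13-point change the ranges are 79–99% against 94–100%. With equal follow-up visits (60, 35, 35, 35), Dunn rejects about 0.1–0.2% of the time.

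**Is baseline the cause?** Hold an 8-point change and correlation 0.5 fixed, and vary only the fall after baseline:

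| Fall after baseline | 0 | 20 | 30 | 40 |
|---|---|---|---|---|
| Dunn-Bonferroni | 56% | 44% | 31% | 24% |

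The signed-rank test stays at 65–67% throughout. Sample size and Bonferroni level are the same in every column, so they do not explain the decline. About 10 points of the gap is present with no fall at all; that part is the general inefficiency of the rank procedure. With a 40-point fall and correlation 0.3, power for 8 points drops to 15%.

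**If only the three follow-up changes are ranked.** Subtracting a patient's baseline does not alter the order of that patient's follow-up values, so k = 3 with 3 pairs at 0.05/3. For the first scenario above, power is 58 / 74 / 93%. With equal visits it rejects 1.1–1.5% against a nominal 1.67%. Part of the recovery comes from the less strict level with fewer pairs.

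**The case against.** The strongest objection is that the defect depends on a reading. The section first defines differences from baseline, then applies the Friedman test to changes and the post hoc test to follow-up times. Ranking three change scores fits those words, and most of the loss then goes. This stands, and the point is conditional on it. Ranking baseline as a visit also fits, so the wording needs settling either way.

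A reader might infer several stronger things that the documents do not support:

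- *That the tests are invalid.* They are conservative. With equal follow-up visits they reject too rarely, so the cost is lost power and no excess of false positives.
- *That the plan will miss the wearing-off of the block.* At 8–9 points it would often do so. A 13-point change is found with 79–99% power. At a correlation of 0.8, even 8 points is found about 75% of the time or more.
- *That the trial's question is compromised.* The stated hypothesis is between-arm non-inferiority. Fading from week 4 to week 12 is nowhere named as a hypothesis.
- *That nothing else in the plan speaks to durability.* Means and SDs are to be presented, there is a week 12 responder definition, and baseline against week 12 belongs to the same family of tests, with about 96–100% power in the three tabulated scenarios.
- *That VAS is much worse affected.* With five ranked visits and 10 pairs, the mean-rank difference needed rises to 2.807 × √(30/240) = 0.99. But the plan does not say that the 1-hour reading is ranked, and it gives no VAS standard deviation. Power figures for VAS would have to borrow the SPADI value, so none are relied on here.

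Two further cautions hold. The plan does not say that 15.3 is a per-visit SD. The 9-point margin is a between-arm quantity, used here only as a reference size.

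**Conclusion.** The point holds as a minor improvement to a secondary within-arm analysis. The inflated standard error follows from algebra once baseline is ranked and most patients improve. The size of the power loss rests on assumed visit means, a post-baseline fall of about 25–40 points, correlations of 0.3–0.7, normality, and 15.3 as the SD at each visit. Under those assumptions the loss is material for changes near the lower end of the cited MCID range. It shrinks for larger changes and higher correlations, and is mostly absent if only follow-up changes are ranked. Neither the between-group primary comparison nor the sample size is touched.

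**What to change.** Replace the Dunn-Bonferroni sentence with:

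> Pairwise visit comparisons within each arm will use the Wilcoxon signed-rank test (or paired t-test) on the two visits concerned, Bonferroni-adjusted over the visit pairs, and the mean paired difference with its 95% confidence interval will be reported.

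State which pairs are compared (6 if baseline is included, 3 if not) and whether the 1-hour VAS reading is one of the visits. Present the results as a description of time course within each arm, not as a comparison of the two approaches. If the Friedman and Dunn procedure is kept, say explicitly that only the follow-up visits are ranked.

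The cost is a sentence or two of wording and a different standard SPSS procedure, with no new data. The signed-rank test assumes roughly symmetric paired differences, a mild requirement for SPADI changes at this sample size. The document describes the study in the past tense, so if the Dunn-Bonferroni results have already been seen, the paired tests should be labelled as added afterwards and reported beside them.

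### Between-group tests carry no multiplicity control and no single SPADI comparison is fixed as confirmatory, so chance significant differences between the approaches are likely

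*Combined protocol and SAP*

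**What the plan says.** Outcome Measures names SPADI as the primary measure and lists the secondary measures as VAS, "active range of motion of the shoulder (ROM), pressure pain thresholds (PPT), and treatment satisfaction". Assessments take place "before injection (baseline) and at 1, 4, and 12 weeks after injection". SPADI yields three scores (pain, disability, total). The success definition uses the total score at week 12, but no score or visit is singled out for the comparison of SPADI scores between groups.

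Statistical Analyses states that for numerical data "the differences between groups were compared using the independent samples t-test or the Mann-Whitney U test", and that "Categorical data were analyzed using chi-square tests or Fisher's exact test". Changes from baseline to the follow-up points "were calculated and included in the intergroup comparison". Within each arm, "The Friedmann test was used for intragroup comparisons of the changes in outcome measures from baseline to follow-up times", and "The post hoc Dunn-Bonferroni test was then used for" pairs of follow-up times. One threshold closes the section: "A P value less than 0.05 was considered statistically significant". The same section sizes the trial for a single non-inferiority comparison on SPADI with a 9-point margin.

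**The concern.** The trial asks how one injection approach compares with the other. Each between-group test that bears on this question is judged at 0.05 by itself, and the plan does not say which test decides. The only multiplicity correction concerns change over time within an arm, which says nothing about the difference between approaches.

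Two things are at stake. Within SPADI, several scores and visits could each supply the headline result. Among the secondary measures, a chance difference at one algometer site, one direction of movement or one visit would be called statistically significant on the same footing as the primary outcome. It could then be read as conflicting with, or adding to, the SPADI conclusion.

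**Working it through.** **The plan's own figure.** The only numerical design target is the sample size. With margin 9, SD 15.3, 80% power, type 1 error 0.05 and no true difference:

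n per group = 2 × [15.3 × (1.645 + 0.842) / 9]² = 35.7, rounded up to 36; 36 / 0.90 = 40.

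This reproduces 36 and 40 per group, with 0.05 taken as one-sided. It is the size for one comparison, so the trial was planned around a single test.

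**Counting the tests** (from Outcome Measures and Statistical Analyses):

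- Secondary numerical measures: 2 VAS (night, activity) + 4 ROM directions + 4 PPT sites = 10.
- Follow-up visits: 3.
- Values only, or changes only: 10 × 3 = 30 tests. Both: 30 × 2 = 60.
- One SPADI score, as value and change: 3 × 2 = 6. All three scores: 18.

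The 1-hour VAS, satisfaction, treatment success, analgesic use, exercise compliance and adverse events are left out and could only add to the count.

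**Expected false positives.** With no true difference this is 0.05 × the number of tests, whatever the correlation: 60 × 0.05 = 3.0; 30 × 0.05 = 1.5.

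**Chance of at least one, if tests were independent** (1 − 0.95^k): k = 6 gives 26.5%; k = 30 gives 78.5%; k = 60 gives 95.4%. The tests are not independent, since they share patients, visits and baseline values, so these figures are only a reference.

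**Chance of at least one, with correlation.** The documents give no correlations, so these are assumptions. Simulation: 40 per group, normal data, no true difference, two-sided t-tests at 0.05, equal correlation between measures and between visits (baseline included), 4,000 null trials per setting.

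| Between measures | Between visits | Values only (30) | Changes only (30) | Both (60) |
|---|---|---|---|---|
| 0.2 | 0.5 | 71% | 71% | 90% |
| 0.5 | 0.5 | 59% | 59% | 81% |
| 0.5 | 0.8 | 48% | 59% | 77% |
| 0.7 | 0.7 | 41% | 46% | 65% |
| 0.8 | 0.8 | 30% | 40% | 56% |

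**One SPADI score alone.** At between-visit correlations of 0.5 to 0.8, testing values at three visits gives 10–13%. Testing values and changes (6 tests) gives 21–22%, or about 20%. If pain and disability scores are also open to choice, the risk is higher.

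**The case against.** The strongest reply is that the plan does have a hierarchy: one measure is primary, the rest are called secondary, and the sample size rests on SPADI alone. Many trials leave secondary outcomes unadjusted when they are treated as supportive. That stands, and it limits the damage to the main conclusion. It does not remove the problem, because the hierarchy stops at the instrument. The SPADI score and visit are left open, and the secondary results get the same significance label as the primary.

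A second reply is that 60 tests is an inference. The text says changes enter the intergroup comparison; it does not say that every value and every change gets its own test. This also stands, and it is why the 30-test range is given. Value and change tests of one outcome at one visit are two looks at much the same difference, so false positives come in clusters and the 3 expected are not 3 separate findings.

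A reader might infer that a false difference is near certain. The documents do not support that: it would need close to the full set of tests, near-independence and no true difference on any measure. A reader might also infer that a chance secondary difference means a false non-inferiority conclusion. It does not. Non-inferiority turns on SPADI against the 9-point margin, and nothing in the text says a secondary P value would decide it.

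**Conclusion.** The point holds as a matter of likelihood. The between-group tests are unadjusted, the only correction answers a different question, and the confirmatory SPADI comparison is not fixed. With no true difference, the chance of a false significant result is about 20% for one SPADI score across three visits as value and change. For at least one of 60 secondary tests it is about 56–90%, and for 30 tests about 30–71%. These ranges rest on assumed correlations (0.2–0.8 between measures, 0.5–0.8 between visits), 40 per group, t-tests throughout and no true difference on any measure. Even the low end is well above 5%. Naming SPADI as primary reduces the consequence for the main conclusion but does not remove the risk within SPADI. This is a cheap improvement; it does not undermine the design.

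**What to change.** Name one SPADI comparison as the sole confirmatory test. Total score at week 12 is a natural example, because the success definition already uses that score and visit. Judge it against the stated 9-point margin at the error level used for the sample size. Since the section is written in the past tense, give the success definition as the reason for the choice, so that it does not appear to follow the results.

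Report all other between-group results (other SPADI scores and visits, VAS, ROM, PPT, satisfaction) as differences with 95% intervals, labelled exploratory and not called statistically significant. Formal adjustment across the secondary outcomes is then optional.

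The cost is wording and reporting. The sample size stays at 36 per group, 40 with dropout. By contrast, making SPADI confirmatory at several points under Bonferroni, with the same margin and SD, would need 51 per group for 3 tests or 67 for 9, before dropout. The downside is that isolated secondary P values can no longer be presented as findings.
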